### Step 4: Determine of the start date of ARV regimen

- The start date of DTG+DESCOVY (D1\_DTG+DESCOVY) after taking into account all 2 components of DTG, DESCOVY is the latest start date of D1\_DTG, D1\_DESCOVY
- The start date of DTG+ TRUVADA (D1\_DTG+TRUVADA)after taking into account all 2 components of DTG, DESCOVY is the latest start date of D1\_DTG, D1\_TRUVADA

#### 13) Toxicity Grades:

- a) For toxicity grade summaries, include all post-baseline graded results up to 30 days after the last dose of study drug, not just those used in by-visit summaries.
- b) For glucose grading, as specified in SAP Section 7.2.2.1, the treatment-emergent flag cannot be determined for nonfasting glucose (including glucose results without a known fasting status). As a result, these records will be excluded from the "Maximum Treatment-emergent Toxicity Grade" summary in the "Treatment-emergent Laboratory Abnormalities" or "Treatment-emergent Grade 3 or 4 Laboratory Abnormalities" summary tables. In addition, fasting glucose and non-fasting glucose will be listed as two separate laboratory tests in the "Laboratory Abnormalities" and "Grade 3 or 4 Laboratory Abnormalities" listings. Only a maximum postbaseline toxicity flag will be displayed and the treatment-emergent flag will not be displayed for nonfasting glucose as the treatment-emergent flag cannot be determined for nonfasting glucose.

   tables trtgrp*response/fisher; /*p value from Fisher's exact test*/
run;
```

f) Homogeneity test: Homogeneity Test of Treatment Effect (HIV-1 RNA < 50 copies/mL by US FDA-defined snapshot algorithm) Across Region in HIV-1 RNA < 50 copies/mL at Week 48 (Snapshot Algorithm). For each region, the odds ratio and its 95% CI are calculated from the CMH test. For overall, the odds ratio and its 95% CI are calculated based on the common odds ratio estimate from the CMH test. The p-value for the homogeneity test is based on the Breslow-Day test of the interaction between region and treatment group as follows.

```
proc freq data=xxx;
  tables region*trtgrp* response /all; /*p value from Breslow Day test,
  (trtgrp: 1, 2; response: 1: < 50, 2: >=50)*/
run;
```

g) Subgroup analyses for HIV-1 RNA < 50 copies/mL by US FDA-defined snapshot algorithm

For the subgroups of age, sex, race, baseline CD4 cell count, and study drug adherence, the proportion difference between two treatment groups and its 95% CIs are calculated based on an unconditional exact method using 2 inverted 1-sided tests, similarly to that for the primary efficacy endpoint.

- h) Homogeneity test: Homogeneity Test of Treatment Effect (HIV-1 RNA < 50 copies/mL by US FDA-defined snapshot algorithm) between Subgroups in HIV-1 RNA < 50 copies/mL at Week 48 (Snapshot Algorithm)
  - a. For the subgroups of age, sex, race, region and study drug adherence, the odds ratio and the associated 95% CIs are estimated for the response variable (response; coded as 1 for success and 0 for non-success) using a logistic regression model including subgroup factor (coded as 1 for the first subgroup and 2 for the second subgroup), treatment (trtgrp; coded as 1 for active [ie, B/F/TAF] and 2 for control), and treatment by subgroup factor.

```
eg. region stratum (region; coded as 1 for "US" and 2 for "Ex-US")
```

For example, for the age subgroup (agegrp; coded as 1 for < 50 and 2 for >= 50), the following SAS code will be used to generate the Odds Ratio and its 95% CI within the subgroup:

Note: For the following code, it is assumed that none of the variables have any formats applied to them. If they do, they must be removed before calling the code.

e.g. for the age subgroup, the following codes will be used to get Odds Ratio and 95% CI within subgroup:

```
proc genmod data=data descending; /*model for success*/
class trtgrpn agegrp;
model response = trtgrpn agegrp trtgrpn*agegrp/dist=bin
link=logit lrci;
estimate 'Group 1' trtgrpn 1 -1 trtgrpn*agegrp 1 0 -1 0/exp;
estimate 'Group 2' trtgrpn 1 -1 trtgrpn*agegrp 0 1 0 -1/exp;
run;
```

Note: trtgrpn is the numeric treatment group variable, response is the response outcome variable (1 vs 0 ('<50' vs'>=50')), agegrp is the subgroup variable for age (1:<50 vs 2: >=50).

(P-value for the homogeneity test was based on the Wald test of the interaction between treatment and subgroup. Odds ratio is from L'Beta estimate, its 95%CI is from L'Beta confidence limits for each subgroup.)

i) ANOVA model for continuous efficacy variable (eg, CD4): The differences in changes from baseline in CD4 cell count between treatment groups and the associated 95% CI will be constructed using an ANOVA, including treatment as fixed effect in the model.

```
proc glm data=adeff;
     class trtgrp;
     model CD4=trtgrp;
     lsmeans trtgrp /alpha=0.05 cl pdiff;
run;
```

j) Listing for US FDA-defined snapshot outcome:

In addition to flagging the values of HIV-1 RNA < 50 or  $\ge 50$  copies/mL for virologic outcomes, flag the last available HIV-1 RNA value while on treatment for the following categories:

- i) HIV-1 RNA >= 50 copies/mL Discontinued Study Drug Due to AE or Death and Last Available HIV-1 RNA >= 50 copies/mL
- ii) HIV-1 RNA >= 50 copies/mL Discontinued Study Drug Due to Other reason\* and Last Available HIV-1 RNA >= 50 copies/mL
- iii) No virologic Data Discontinued Study Drug Due to AE or Death and Last Available HIV-1 RNA < 50 copies/mL
- iv) No virologic Data Discontinued Study Drug Due to Other reason\* and Last Available HIV-1 RNA < 50 copies/mL
- Note: \* Other reasons include subjects who discontinued study drug due to investigator's discretion, subject decision, lost to follow-up, noncompliance with study drug, protocol violation, pregnancy, and study terminated by sponsor.
- 15) Clarification of the following LOCF algorithms:
  - Baseline values will be carried forward.
  - For CD4:

If a value is missing in an analysis visit window, replace the missing value with the last on-treatment value observed before the analysis visit window that has the missing value.

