#### Randomization

Subjects will be randomized in a 1:1 ratio to 1 of 2 treatment groups (Treatment Group 1: Treatment Group 2). Randomization will be stratified by prior NRTI use (F/TAF vs. F/TDF) and documented or suspected history of NRTI resistance.

NRTI resistance will be stratified by the following categories:

- 1) K65R/E/N, or 3 or more thymidine analogue mutations (TAMs) that include M41L or L210W, or T69 insertions (TAMs are: M41L, D67N, K70R, L210W, T215F/Y, and K219Q/E/R/N)
- 2) Any other pattern of NRTI resistance of M41L, D67N, K70R, L74I/V, Y115F, Q151M, M184I/V, L210W, T215F/Y, K219Q/E/R/N, T69D, K70E/G/M/Q/S/T, V75A/S/M/T
- 3) None of these mutations/no NRTI resistance

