### All B/F/TAF Analysis:

- For subjects who receive B/F/TAF in the randomized phase, all available data collected from both randomized phase and OL extension phase (if applicable) will be included in the all B/F/TAF analysis.
- For subjects who receive DTG + F/TAF in the randomized phase and receive at least 1 dose of B/F/TAF in the extension phase, (1) all available AE, concomitant medication, pregnancy, and death data with start date **on or after** the first dose date of B/F/TAF in the extension phase and (2) all available other data, such as laboratory, vital sign, and ECG data, collected **after** the first dose date of B/F/TAF in the extension phase will be included, except that the data collected **on or prior to** the first dose date of B/F/TAF will be used to derive the baseline value for the all B/F/TAF analysis.

Note that all data for subjects who receive DTG + F/TAF in the randomized phase and do not receive any dose of B/F/TAF in the extension phase will be excluded from all B/F/TAF analysis. The actual treatment received will differ from the randomized treatment only when the actual treatment received differs from randomized treatment for the entire treatment duration.

Analysis results will be presented using descriptive statistics. For categorical variables, the number and percentage of subjects in each category will be presented; for continuous variables, the number of subjects (n), mean, standard deviation (SD) or standard error (SE), median, first quartile (Q1), third quartile (Q3), minimum, and maximum will be presented.

All statistical tests will be 2-sided and performed at the 5% significance level unless otherwise specified.

By-subject listings will be presented for all subjects in the All Randomized analysis set unless otherwise specified, and sorted by subject identification (ID) number, visit date, and time (if applicable). Data collected on log forms, such as AEs, will be presented in chronological order within a subject. The treatment group to which subjects were randomized will be used in the listings.

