#### 6.1.2. Secondary Efficacy Endpoints

6.1.2.1. Definition of the Secondary Efficacy Endpoints

The secondary efficacy endpoints include:

- The proportion of subjects with HIV-1 RNA < 50 copies/mL at Week 48 as determined by the US FDA-defined snapshot algorithm
- The change from baseline in CD4+ cell count at Week 48

The analyses for the secondary efficacy endpoints will be conducted using the FAS and the Week 48 PP analysis set, respectively.

- 6.1.2.2. Analysis of the Secondary Efficacy Endpoints
- 6.1.2.2.1. Analysis of the Proportion of Subjects with HIV-1 RNA < 50 copies/mL as Determined by US FDA-defined Snapshot Algorithm

The proportion of subjects with HIV-1 RNA < 50 copies/mL at Week 48 will also be analyzed by the US FDA-defined snapshot algorithm based on the FAS and Week 48 PP analysis set, respectively.

Proportion of subjects with HIV-1 RNA < 50 copies/mL at Week 48 as determined by US FDA-defined snapshot algorithm will be analyzed similarly to the primary efficacy endpoint. However, the noninferiority margin used for the proportion of subjects with HIV-1 RNA < 50 copies/mL will be 10%.

Similarly to the primary efficacy endpoint, noninferiority will be assessed using the conventional CI approach. The point estimate of treatment difference (B/F/TAF group – DTG+F/TAF group) in the percentage of subjects with HIV-1 RNA < 50 copies/mL and the associated 2-sided 95.001% CI will be constructed based on an unconditional exact method using 2 inverted 1-sided tests.

It will be concluded that B/F/TAF is noninferior to DTG+F/TAF if the lower bound of the 2-sided 95.001% CI of the difference between treatment groups (B/F/TAF group – DTG+F/TAF group) in the percentage of subjects with HIV-1 RNA < 50 copies/mL is greater than –10%.

The above analysis will be performed using both the FAS and the Week 48 PP analysis set.

In addition, the following analyses will be performed using the FAS to evaluate the interaction between region and treatment to assess homogeneity of treatment effect across different regions.

A region is defined as multiple sites combined based on geographical locations (see Appendix 2 for region definition).

For each region, the difference in the proportion of subjects with HIV-1 RNA < 50 copies/mL between treatment groups and its 95% CI will be calculated based on an unconditional exact method using 2 inverted 1-sided tests.

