The CMH analysis will be used to estimate the odds ratio and corresponding 95% CI for each region and overall. The homogeneity of the odds ratios across different regions will be tested using a Breslow-Day test and a corresponding p value will be reported.

6.1.2.2.2. Subgroup Analysis of the Proportion of Subjects with HIV-1 RNA < 50 copies/mL at Week 48 as Determined by US FDA-defined Snapshot Algorithm

Since the proportion of subjects with HIV-1 RNA  $\geq$  50 copies/mL at Week 48 as determined by the US FDA-defined snapshot algorithm (primary endpoint) is expected to be very low (around 2%), the efficacy analysis by subgroup will be conducted by assessing the proportion of subjects with HIV-1 RNA < 50 copies/mL determined by the US FDA-defined snapshot algorithm at Week 48 (a secondary efficacy endpoint) within each subgroup specified in Section 3.4.1 based on the FAS for randomized phase analysis.

For each level of subgroup factors, the proportion difference between treatment groups and the associated 2-sided 95% CIs will be computed based on an unconditional exact method using 2 inverted 1-sided tests.

Additionally, a logistic regression model will be performed which include subgroup, treatment, and treatment by subgroup interaction. The odds ratio and the associated 95% CI will be estimated within each subgroup. The homogeneity of the treatment effects between subgroups will be evaluated using a Wald test based on the interaction between treatment and the subgroup factor.

A forest plot of the treatment differences in HIV-1 RNA < 50 copies/mL (US FDA-defined snapshot algorithm) at Week 48 and their associated 95% CIs for each subgroup will be generated.

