# **Appendix 3.** Region Definition

Region	Country Name	State	No. of Subjects in Safety Analysis Set or FAS (N=565)	Total No. of Subjects by Region in Safety Analysis Set or FAS Set (N=565)
Region 1	CANADA (CAN)		49	49
	AUSTRIA (AUT)		3	85
Region 2	FRANCE (FRA)		26	
	GERMANY (DEU)		56	
	United States (USA)	CA	63	83
Region 3	United States	HI	4	
	United States	WA	16	
	United States	AZ	3	64
Danian 4	United States	СО	2	
Region 4	United States	NM	6	
	United States	TX	53	
	United States	KY	6	33
D 5	United States	MI	3	
Region 5	United States	MN	12	
	United States	MO	12	
	United States	DC	28	82
Danien (	United States	MA	35	
Region 6	United States	NJ	4	
	United States	NY	15	
	United States	GA	31	67
D : 7	United States	LA	0	
Region 7	United States	NC	33	
	United States	SC	3	
Pagion 0	United States	FL	70	102
Region 8	United States	PR*	32	

\* PR = Puerto Rico.

Note: In general, a region is defined as multiple sites combined based on geographical locations. For example, for international studies, sites from each country or multiple neighboring counties were combined; and for US studies, sites from each state or multiple neighboring states were combined.

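### The treatment-by-region homogeneity test is asymptotic although non-responders will be sparse across eight regions; adding Zelen's exact p-value is a cheap, minor improvement

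*SAP*

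**What the plan says.** SAP 6.1.2.2.1 plans analyses in the FAS to "evaluate the interaction between region and treatment to assess homogeneity of treatment effect across different regions". Three outputs are specified for the proportion with HIV-1 RNA below 50 copies/mL at Week 48:

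- For each region, the treatment difference with a 95% CI by the unconditional exact method.
- For each region and overall, an odds ratio with a 95% CI from the CMH analysis.
- A homogeneity test: "The homogeneity of the odds ratios across different regions will be tested using a Breslow-Day test and a corresponding p value will be reported".

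Item 14f of SAP Appendix 8 repeats the choice of test: "The p-value for the homogeneity test is based on the Breslow-Day test of the interaction between region and treatment group as follows". Its PROC FREQ step reads "tables region*trtgrp* response /all; /*p value from Breslow Day test" and has no EXACT statement. The general level is set in SAP section 3: "All statistical tests will be 2-sided and performed at the 5% significance level unless otherwise specified".

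SAP Appendix 3 lists eight regions with 49, 85, 83, 64, 33, 82, 67 and 102 subjects, 565 in all. Neither section attaches a decision rule to the homogeneity p-value, and neither says what to do when a regional odds ratio cannot be calculated.

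**The concern.** Breslow-Day refers its statistic to a chi-square distribution, which needs reasonable expected counts in every region. In a virologically suppressed population the non-responder column will be thin in all eight.

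The SAP accepts this argument elsewhere. Section 1.4 moves the primary analysis from a normal approximation to an exact method because the event proportion was very low, and section 6.1.2.2.1 uses exact intervals for the regional differences. The homogeneity p-value and the regional odds ratios stay asymptotic, in much smaller strata.

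If the test is conservative, its error leans towards a large p-value, which is the reassuring direction for a check of regional consistency. In addition, some regional odds ratios that item 14f requires will not exist.

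**Working it through.** **The SAP's own exact-versus-normal figures.** The SAP gives no size or power for the Breslow-Day test, so there is nothing to reproduce for it directly. Its figures for the primary test do reproduce. With 2% in both arms, a 4% margin, one-sided 0.025 and 260 per arm, the normal approximation gives 0.04 / √(2 × 0.02 × 0.98 / 260) − 1.96 = 1.30, which is 90.3% power. Full enumeration of the unconditional exact score test at 282 and 283 per arm gives 85.4%, matching the stated 85%.

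**Inputs.**
- Region sizes come from SAP Appendix 3. Each region is split about in half, because SAP 1.2 has "Subjects will be randomized in a 1:1 ratio to 1 of 2 treatment groups". Randomization was not stratified by region, so this is an approximation.
- The non-response rate p is an assumption. Non-response here is HIV-1 RNA of at least 50 copies/mL (around 2% by SAP 6.1.2.2.2) plus the no-virologic-data category of SAP 6.1.1.2, so p lies above about 2%.
- The only Week 48 figures for this endpoint in the documents are from the Phase 2 study in treatment-naive subjects (protocol 1.2.3.3): (2 + 3) / (65 + 33) = 5/98 = 5.1%. That is an anchor only, because the population differs.

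**Expected cells.** The mean non-responder cell is 565p/16: 0.7 at 2%, 1.8 at 5%, 2.5 at 7% and 3.5 at 10%. At 5% the cells range from 16 × 0.05 = 0.8 to 51 × 0.05 = 2.6, so none of the 16 reaches 5. At 10% only the largest region does (51 × 0.10 = 5.1). The simulated share of cells holding 0 to 3 is 99%, 89%, 75% and 53% at 2%, 5%, 7% and 10%, and 41% at 12%.

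**Size of Breslow-Day.** The statistic is Σ(xⱼ − Eⱼ)²/Vⱼ. Here xⱼ is the count in one arm of region j, Eⱼ is its fitted value at the Mantel-Haenszel common odds ratio with margins fixed, and Vⱼ is the inverse of the sum of reciprocals of the four fitted cells. Regions with no non-responder were dropped, and degrees of freedom were the remaining regions minus one. With 200,000 trials per rate and no true heterogeneity:

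| Non-response | 2% | 3% | 4% | 5% | 7% | 10% | 15% |
|---|---|---|---|---|---|---|---|
| True size at nominal 5% | 1.2% | 1.8% | 2.5% | 3.1% | 3.9% | 4.4% | 5.0% |

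A separate simulation gave 1.1%, 2.1%, 3.0%, 4.0% and 4.5% at 2%, 3%, 5%, 7% and 10%. Fixing the degrees of freedom at 7 lowers size further (0.2%, 2.4%, 3.6% and 4.3% at 2%, 5%, 7% and 10%). The Tarone adjustment makes no material difference.

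**Zelen's exact test on the same tables.** Size is 4.1%, 5.3%, 5.2% and 5.1% at 2%, 5.1%, 8% and 10%, with Monte Carlo error of about 0.25 points. Power, Breslow-Day then Zelen:

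| Pattern | 2% | 4% | 5% | 7% | 10% |
|---|---|---|---|---|---|
| Odds ratios alternating 3 and 1/3 | 8 → 22% | 32 → 42% | 44 → 51% | 62 → 65% | 82 → 83% |
| Region of 102 with odds ratio 6 | 16 → 26% | 28 → 42% | 34 → 46% | 47 → 56% | 59 → 65% |

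For moderate heterogeneity (odds ratios alternating 2 and 1/2), power is 15 → 21% at 5.1% and 28 → 30% at 8%.

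**Regional odds ratios.** The expected number of regions with at least one arm free of non-responders is Σⱼ[1 − (1 − (1−p)^n₁ⱼ)(1 − (1−p)^n₂ⱼ)]. At p = 5%, the region of 33 (16 and 17 per arm) contributes 1 − 0.560 × 0.582 = 0.67 and the region of 102 contributes 1 − 0.927² = 0.14. Summed over the eight regions, the total is about 4.6 at 3%, 2.6 at 5% and 1.5 at 7%.

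**The case against.** The strongest reply has four parts.

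1. **Conservatism depends on an unstated rate.** A reader might infer that the test runs far below its 5% level. That holds only at about 2 to 4% non-response, which is close to the rate of 50 copies/mL or more on its own, whereas this endpoint also counts missing virologic data. At the Phase 2 anchor of 5.1% the size is 3.1%, and by 10% it is nearly nominal. This part stands, so the finding must carry its assumed rate.
2. **Changing the test does not cure the shortage of information.** With moderate heterogeneity both tests will usually miss it, because non-responders are few. This stands too, and a large Zelen p-value would also be weak evidence.
3. **Nothing depends on the p-value.** A reader might infer that it will support a claim of consistent effect, or that the non-inferiority conclusion is at risk. The SAP only says that the p-value is reported. It states no such claim, and the test concerns a secondary endpoint. The exact regional differences and the separate US versus Ex-US interaction test are also planned, so regional consistency does not rest on Breslow-Day alone.
4. **Timing.** SAP 2.2.1 describes the Week 48 analysis as already done, and this SAP governs the final analysis. Replacing the test now would be a post hoc change to a Week 48 result. This argues for adding the exact test, not substituting it.

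What survives is that the approximation is a poor fit to these tables over the lower part of the plausible range, that an exact version is readily available, and that the plan has no rule for odds ratios that do not exist.

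**Conclusion.** This is a minor point and a cheap improvement. Breslow-Day is conservative here by an amount that depends on the non-response rate: markedly so at 2 to 4%, moderately at 5 to 7%, and hardly at all at 10% or more. Zelen's test brings the level close to nominal. In the two strong patterns tabulated it gains roughly 6 to 14 points of power at 4 to 5% non-response and about 1 to 9 points at 7 to 10%. Those gains are for large departures; for moderate ones, power is low with either test.

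The undefined regional odds ratios are a separate practical gap, expected in about 4.6, 2.6 and 1.5 of the eight regions at 3%, 5% and 7%.

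These figures rest on the Appendix 3 region sizes, roughly equal arms within each region, a common non-response rate under the null, and the assumed rates shown. The documents do not support reading this as a threat to the primary analysis or its conclusion.

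**What to change.** - In Appendix 8 item 14f, add `exact eqor;` to the PROC FREQ step. In SAP 6.1.2.2.1, say that Zelen's exact p-value is reported beside the Breslow-Day one, and record that it was added after the Week 48 analysis.
- Use the unconditional exact regional differences, already specified, as the main regional display.
- For regional odds ratios, give exact CIs, or mark the odds ratio as not estimable where an arm has no non-responder.
- State that a non-significant homogeneity p-value is not evidence of a uniform effect across regions.

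The cost is a few sentences of text, one line of code for the test and a small change to the odds-ratio output; no new data are needed. The downside is a small post hoc addition that must be disclosed, and a second p-value that may differ from the one produced at Week 48.

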#### 16) TEAE

## **Events with Missing Onset Day and/or Month**

An event is treatment emergent if the following 3 criteria are met:

- 1) The month and year (or year) of onset date is the same as or after the month and year (or year) of the first dose of study drug, and
- 2) The month and year (or year) of the onset date is the same as or before the month and year (or year) of the 30th day after the date of the last dose of study drug, and
- 3) End date is as follows:
  - a) The (complete) end date is on or after the first dose date, or
  - b) The month and year (or year) of end date is the same or after the month and year (or year) of the first dose of study drug, or
  - c) End date is completely missing

